8.7.2 Additional analyses of the incidence of MAS

8.7.2.1 Analysis of first occurrence and recurrence of MAS

The incidence rate of MAS will also be analyzed with respect to 1st occurrence and recurrence respectively. The rationale for this is to account for a biological distinction in altered risk following a first event. For the analyses, the 1st occurrence of MAS is defined to occur at or after baseline regardless of whether the patient had a history of MAS or not. The patients included in the risk set for a 2nd occurrence of MAS are only those who had a 1st occurrence of MAS as defined above. Likewise, the patients included in the risk set for a 3rd occurrence of MAS are only those who had a 2nd occurrence of MAS etc. MAS events and patient-time will only be counted during Kineret treatment exposure that includes an additional period of 2 days after treatment stop.

8.7.2.2 Analysis of the duration until the incidence of MAS

The number of days from first injection with Kineret (baseline) until the first occurrence of MAS will be presented for the MAS-1 set. The number of MAS events and percentages will be presented grouped by simultaneous Kineret treatment (Yes/No) and days since first injection with Kineret treatment (1-30 days, 31-180 days, 181-365 and >365 days).

In addition, the time from discontinuation of Kineret until the first occurrence of MAS will be summarized for the MAS-1 set. The number of events and percentages will be presented grouped by “still treated” and subsequently 10 day intervals since discontinuation of Kineret.

In the time to event analyses, all MAS events occurring after baseline will be counted regardless of whether patients are under simultaneous Kineret treatment exposure or not. Notwithstanding, in reporting it will be indicated whether simultaneous Kineret treatment exposure was present at the occurrence of the event.

8.7.2.3 Kaplan-Meier cumulative probability curve of MAS

The cumulative probability of a first event of MAS over time will be estimated for the complete set and graphically presented as a Kaplan-Meier curve.

In addition, a Kaplan-Meier cumulative probability curve stratified by history of MAS at baseline (Yes/No) will be presented. In the case of too few patients in either of the subgroups (number of patients ≤ 10), the stratified analysis should be dismissed from the CSR.

Patients should be censored at 2 days after discontinuation of Kineret treatment, if they die for other reasons than MAS (no 2 days addition), if they are lost to follow-up, or if they have still not experienced a MAS event at the last visit.

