Data analysis	
Patient characteristics at baseline will be summarized and presented.
 
The analysis will include calculation of unique incidence rates (with 95% CI) and incidence proportions of each reported term of non-serious AE (moderate and severe) and SAE. A patient may contribute with multiple events of the same AE term. AE specific incidence rates and proportions will be presented overall for the whole study period and also by time windows defined with reference to the first dose of Kineret following a SJIA diagnosis. Analyses of sub-populations with long-term Kineret treatment will enable descriptive comparisons of incidence early in the treatment cycle and incidence resulting from long-term treatment.
 
This study will pay a special interest to the incidence of MAS. Therefore, the time to event since start of Kineret treatment, in this scenario regardless of whether the patient was on Kineret treatment when the event occurred, and the cumulative probability of a first MAS event over time will be analyzed. Trigger events associated with each MAS episodes will be summarized.
 
Summary statistics for the duration of Kineret treatment will be presented overall and by time window.
 
The reasons for Kineret treatment discontinuation will be summarized with number and percentage. Use of other SJIA related medications at baseline and concomitantly with Kineret treatment will be summarized by treatment patterns.

Milestones	
The data extraction from the Pharmachild JIA registry is planned to start in March, 2019 and end in April, 2019. A final study report is planned for October, 2019.

4 Amendments and updates

None.

5 Milestones

This PASS is based on secondary use of data, utilizing already available data from the Pharmachild JIA registry. In the Pharmachild registry data has been collected since 2011. Data collected up until September 30, 2018 will be used in this study. The data extraction from the Pharmachild registry will start as soon as the CSP, SAP and contract with PRINTO have been finalized.

Milestone	Planned date
Start of data collection	March, 2019
End of data collection	April, 2019
Registration in the EU PAS register	March, 2019
Final report of study results	October, 2019

6 Rationale and background

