8.7.5 Duration of treatment and reasons for discontinuation

Summary statistics for the duration of Kineret treatment will be presented overall and by time window.

The reasons for Kineret treatment discontinuation for more than 30 days will be summarized with number and percentage. The reasons for discontinuation will be collected as per the Pharmachild CRF: adverse event (moderate/severe/serious event or mild event), intolerance, dose change, inefficacy, remission, surgery, pregnancy or other reason. A patient can contribute with multiple discontinuations if starting a new treatment period after a treatment holiday of more than 30 days. Furthermore, multiple reasons can be recorded for one single discontinuation

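### The Kaplan-Meier curve for first MAS is censored 2 days after Kineret stops, but it is not labelled on-treatment, not reconciled with the neighbouring counting rule, and open to dependent censoring in either direction

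*Protocol*

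**What the plan says.** Protocol section 8.7.2.3 defines the target: "The cumulative probability of a first event of MAS over time will be estimated for the complete set". Follow-up in that curve is cut by this rule: "Patients should be censored at 2 days after discontinuation of Kineret treatment". Death from causes other than MAS, loss to follow-up and reaching the last visit without MAS are also censoring events. The section does not describe the curve as on-treatment. It does not say whether the discontinuation meant is the first stop, the last stop, or only a gap longer than 30 days.

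The section before it, 8.7.2.2, presents timing tables for the MAS-1 set, meaning patients with a first MAS diagnosis after Kineret start. It then states: "In the time to event analyses, all MAS events occurring after baseline will be counted regardless of whether patients are under simultaneous Kineret treatment exposure". Its second table is described as follows: "the time from discontinuation of Kineret until the first occurrence of MAS will be summarized for the MAS-1 set".

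The data analysis part of the abstract (section 3) introduces time to event since the start of Kineret and continues: "in this scenario regardless of whether the patient was on Kineret treatment when the event occurred, and the cumulative probability of a first MAS event".

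Section 8.7.5 lists the recorded reasons for stopping. The list opens with adverse event and continues "intolerance, dose change, inefficacy, remission, surgery, pregnancy or other reason". Section 8.7.2.4 lists the recorded MAS triggers, which include disease flare and treatment changes.

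**The concern.** There are three linked problems.

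1. **Unclear estimand.** A Kaplan-Meier curve is a time-to-event analysis. Taken literally, the 8.7.2.2 rule says a first MAS well after stopping counts, while 8.7.2.3 censors the patient before it. Two programmers could defend different curves.

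2. **Doubtful independence of censoring.** Kaplan-Meier treats a patient censored at stopping as having the same later risk as those still treated. Stops for inefficacy or an adverse event may remove patients at higher MAS risk. Stops in remission may remove patients at lower risk. Section 8.9 discusses exposure misclassification and selection into the long-term sets, but not this.

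3. **No post-stop risk.** The rates, the incidence proportions and the curve all end at exposure plus 2 days. Later first MAS appears only in the MAS-1 tables. Everyone in that set had MAS, so the percentages describe how events are distributed and not how likely they are. Yet the protocol tabulates MAS in 10-day intervals after stopping and records treatment change as a trigger, so it treats the post-stop period as relevant.

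MAS is the study's only event of special interest.

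**Working it through.** **The text.**

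- *Counting window.* Sections 8.7.1, 8.7.2.1, 8.7.2.4, 8.7.3 and 8.7.4 use Kineret exposure plus 2 days. The curve's censoring point matches that window. Section 8.7.2.2 is the exception.
- *Scope of the 8.7.2.2 rule.* That section holds two timing summaries (from first injection and from discontinuation), which is enough to explain its plural wording about analyses. The abstract attaches the regardless-of-treatment phrase to time since start and then names the cumulative probability as a further item. An intended on-treatment curve is therefore tenable, but it is never stated.
- *Restarts.* The footnote in 8.7 and section 8.7.5 expect patients to stop and restart. Section 8.7.2.1 counts first MAS during Kineret exposure without limiting it to the first course. If discontinuation in 8.7.2.3 means the first stop, a first MAS in a second course enters the rate but not the curve. The 30-day allowance for interruptions is given in 8.7.4 for the long-term sets and, as a threshold, in 8.7.5, but not for the curve.

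**The size.** The protocol gives no MAS probability, event count or discontinuation rate, so there is no figure to reproduce. Its only related count is Table 1: 212 + 95 = 307 treated SJIA patients, consistent with the planned 300 or so. All inputs below are assumptions.

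- A and D: MAS hazard 0.04/year and stop hazard 0.5/year for everyone.
- B, C and E: 30% of patients at 0.10/year and 70% at 0.015/year. Stop hazards (high-risk/low-risk) are 1.5/0.3 in B and E, and 0.3/0.8 in C.
- MAS hazard after stopping: unchanged in A, B and C; five times higher for 30 days in D and E, then unchanged. No restarts.

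*Since-start risk at 2 years.* With the hazard unchanged after stopping, it does not depend on who stops.

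- B and C: 1 − 0.3·e^(−0.10×2) − 0.7·e^(−0.015×2) = 1 − 0.2456 − 0.6793 = 7.5%.
- A: 1 − e^(−0.08) = 7.7%.
- D: the extra hazard is 4 × 0.04 = 0.16/year for 30/365.25 = 0.082 year, so a patient who completes that window survives it with factor e^(−0.0131) = 0.987. The share stopping early enough to complete it is 1 − e^(−0.5×1.912) = 0.616. MAS-free survival is about 0.9231 × (1 − 0.616 × 0.0131) = 0.916, or 8.4%.

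*Censored curve at 2 years.* It estimates 1 − exp(−∫h̄(t)dt). Here h̄(t) is the average MAS hazard among patients still at risk, with weights p·exp(−h·t − d·(t − 2 days)), where p is the group's share, h its MAS hazard and d its stop hazard.

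- B: h̄ at 0, 1 and 2 years is 0.0405, 0.0241 and 0.0177, because high-risk patients leave. By Simpson's rule the integral is (0.0405 + 4×0.0241 + 0.0177)/3 = 0.0515, and 1 − e^(−0.0515) = 5.0%.
- C: h̄ is 0.0405, 0.0484 and 0.0571, because low-risk patients leave. The integral is (0.0405 + 4×0.0484 + 0.0571)/3 = 0.0971, which gives 9.2%.
- A and D: h̄ stays at 0.04, which gives 7.7%.
- E has the same curve as B.

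| Scenario | Censored at stop + 2 days | All post-baseline MAS |
|---|---|---|
| A: stopping unrelated to risk, hazard unchanged | 7.7% | 7.7% |
| B: high-risk patients stop more | 5.0% | 7.5% |
| C: low-risk patients stop more | 9.2% | 7.5% |
| D: stopping unrelated to risk, hazard raised after stop | 7.7% | 8.4% |
| E: B plus the raised hazard | 5.0% | 8.4% |

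A simulation of 200,000 patients per scenario agrees within its random error: A 7.8% and 7.8%, B 5.0% and 7.6%, C 9.4% and 7.6%, D 7.6% and 8.4%, E 5.0% and 8.4%. In it, 31% to 60% of first MAS events within 2 years fell after the censoring point.

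B and C isolate dependent censoring: the hazard does not change after stopping, so 7.5% is also the risk had nobody stopped, and the curve misses it in opposite directions. D isolates a difference of question: 7.7% is right for the on-treatment hazard and 8.4% is right for risk since start.

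**The case against.** The strongest defence is that the rule is explicit, can be programmed for a single course, and matches the exposure window used almost everywhere else. The regardless-of-treatment sentence belongs to 8.7.2.2, and the sentence after it, on indicating exposure at the event, fits that section's Yes/No table. The objective concerns Kineret in use, so an on-treatment curve is a legitimate choice. The study is descriptive, without a hypothesis test.

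Most of this stands, and it rules out several stronger readings:

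- A reader might infer an outright contradiction, or that the abstract promises a curve of all MAS events. The wording allows the literal conflict but does not force it, and the abstract does not attach its qualifier to the cumulative probability.
- A reader might take the curve to be the only planned risk estimate for MAS. Section 8.7.3 also plans incidence proportions, overall and by time window, though likewise limited to exposure plus 2 days.
- A reader might assume a raised hazard after stopping and call the resulting gap bias. If stopping is unrelated to risk, as in D, that gap is between two estimands and says nothing about informative censoring.
- A reader might conclude that a since-start curve must replace the planned one. It answers a different question and includes time on other SJIA treatments.

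The defence does not supply a label, a restart rule, any mention of dependent censoring, or a post-stop risk with a denominator.

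**Conclusion.** The point holds as an unlabelled and unreconciled estimand with a plausible, unacknowledged dependence between censoring and MAS risk. That dependence is inferred from the protocol's own stop reasons and MAS triggers; it is likely but not shown. Its direction cannot be settled from the document: under the assumed inputs the 2-year figure is 2.5 percentage points too low (5.0% against 7.5%) or 1.7 too high (9.2% against 7.5%), and there is no gap if stopping is unrelated to risk and the hazard does not change. These figures show only that the choice can matter; they do not predict this registry's result.

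The separate gap is firmer, because it rests on text alone: no planned analysis with an at-risk denominator covers first MAS more than 2 days after stopping. Censoring non-MAS deaths is a lesser matter; no death rate is given, so its effect cannot be sized.

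**What to change.** - Reconcile 8.7.2.2 and 8.7.2.3: either limit the all-events rule to the MAS-1 tables or say which curve it governs.
- Label the existing curve as on-treatment (exposure plus 2 days). State which discontinuation censors, how a restart is treated, and how gaps of up to 30 days are treated.
- Add a second curve for the complete set: time from first injection to first MAS regardless of treatment, ending at last visit, loss to follow-up, data cut-off or non-MAS death. Preferably treat non-MAS death as a competing event (Aalen-Johansen).
- Name dependent censoring in section 8.9 as a limitation of the on-treatment curve, with direction unknown.

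The cost is protocol or SAP wording and one extra figure from data the registry already holds. The downside is that the since-start curve mixes time on and off Kineret, which is why the two should be shown side by side. It should be settled before extraction: sections 8.6 and 9.1 say that only summary output is obtained, so the sponsor could not derive the second curve later from patient-level data.

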8.7.2.4 Trigger events of MAS

For each event of MAS collected as an ESI, a trigger event is recorded in the CRF. The following categories are possible to record: 'Disease flare', 'infection', 'changes of treatment' and 'other'. The 'other' field is supplemented with a free-text field. For the MAS-1 set, a summary table will present the number of MAS events and percentages per category. Depending on available data recorded in the free-text field for the "other" category, more categories may be added to the summary table. Reasons will only be presented for MAS events that occur when patients are on Kineret treatment exposure (including an additional period of 2 days after treatment stop).

8.7.3 Incidence proportions of Adverse events

The incidence proportion (i.e. risk) for each reported AE term will be calculated overall and within time windows by counting the number of patients experiencing the event at or after baseline divided with the number of patients treated with Kineret during the respective period. As regards to the calculation of time window specific incidence proportions, the start date will be set to equal the start date of the time window or when the patient start Kineret treatment within the time window. Only events that occur when patients are on Kineret treatment exposure (including an additional period of 2 days after treatment stop will be counted).

8.7.4 Incidence rates of Adverse events in sub-population

In a sub-population constituting those with more than 12 months of continuous treatment with Kineret, incidence rates of non-serious AEs of at least moderate severity, all serious AEs and MAS will be calculated for the time after 12 months and in addition incidence rates will be retrospectively derived for each preceding time window (i.e. 1-6, 7-12 months). Similarly, the analysis will also be performed for the subgroup of patients that have more than 18 (preceding windows to present: 1-6, 7-12 and 13-18 months) and 24 (preceding windows to present: 1-6, 7-12, 13-18 and 19-24 months) months of continuous treatment with Kineret respectively. These analyses will enable descriptive comparisons of incidence early in the treatment cycle and incidence resulting from long-term treatment. In the interpretation of the incidence rates calculated for the sub-populations, respective incidence rate for the total study population (the complete set) will also be taken into account. Interruptions of treatment, e.g. treatment holidays, will be allowed for up to 30 days with respect to the definition of continuous treatment. Neither AEs nor patient-time will be counted during the interruption.

Only events that occur when patients are on Kineret treatment exposure (including an additional period of 2 days after treatment stop will be counted.

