8.5 Study size

The sample size is not based on any formal calculation. All patients enrolled in the Pharmachild JIA registry study before September 30, 2018 meeting the criteria defined for the study population will be included in the study.

It is estimated that approximately 300 patients may be included.

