8.7.1 Incidence rates of Adverse events

The analyses will include calculation of unique incidence rates (with 95% CI) of each reported non-serious AE (moderate and severe), SAE and MAS as an ESI respectively. A patient may contribute with multiple events of the same AE term. Incidence rate of events (calculated as the number of the incident events divided by the sum of patient years under risk) will be expressed

as incidence rate per 100 patient years. The incidence rate will be derived by a Poisson regression model (with only intercept) and the 95% CI will be estimated using the Poisson estimator with a cluster-robust estimate of variance to control for both overdispersion and intracluster correlation. AE specific incidence rates will be presented overall for the complete study period and by time windows defined with reference to baseline. The time windows will be defined as follows: 1-6 months, 7-12 months, 13-18 months, 19-24 months and >24 months of calendar time. AEs and patient-time will only be counted during Kineret treatment exposure that includes an additional period of 2 days (i.e. slightly longer than 5 half-lives in patients without renal impairment after treatment stop).

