8.9 Limitations of the research methods

An uncontrolled single-armed study design is the only feasible design in this non-interventional study since a fair comparator group would be difficult to introduce given the real-world practice of treatment regimen. Accordingly, the study design carries the general limitations inherent in an uncontrolled design regarding statistical analyses, interpretation, generalizability and conclusiveness. The incidence rates for AEs while exposed to Kineret may be under or overestimated because of exposure-related misclassification of patient-time. The direction of the bias will depend on the direction of the difference in true incidence in the non-exposed (all other treatment options) group vs. Kineret exposed group (e.g. a higher incidence in non-exposed vs. exposed will over-estimate the incidence rates for the Kineret treatment). The non-exposed patient-time will likely be a mixture of other SJIA-related medications. Misclassification of exposure is likely during non-registered short interruptions of Kineret treatment. Nevertheless, by using a validly conducted register study with the primary objective to research the adverse effects of JIA related medications and with granular recording of exposure time will alleviate the magnitude of the potential exposure misclassification bias.

The use of sub-populations with patients treated for a certain time may bias the comparisons since the selected patients may have been selected because of a relatively low incidence of adverse events before selection into the sub-population. The probability of experiencing an adverse event by chance may be increased following selection into the sub-population. A comparison with the incidence rate for the respective time window in the total population (the complete set) and not only the sub-population specific incidence rate will likely alleviate a more unbiased conclusion.

All patients in the Pharmachild registry with a diagnosis of SJIA (as per ILAR classification criteria) and who were ever treated with Kineret following the SJIA diagnosis will be included in

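### In 8.7.4 the exclusion of allowed interruptions conflicts with the plan's own 2-day post-stop exposure period, so long-term sets and complete set may count the first two undosed days differently (minor)

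*Protocol*

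**What the plan says.** Protocol 8.7.4 defines continuous treatment for the long-term sets: "Interruptions of treatment, e.g. treatment holidays, will be allowed for up to 30 days with respect to the definition of continuous treatment". It then gives the counting rule for those gaps, without exception: "Neither AEs nor patient-time will be counted during the interruption". The section closes with a second rule: "Only events that occur when patients are on Kineret treatment exposure (including an additional period of 2 days after treatment stop will be counted". That sentence names events and is silent on patient-time. "Treatment stop" is not defined.

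Section 8.7.1, which governs the overall rates, states: "AEs and patient-time will only be counted during Kineret treatment exposure that includes an additional period of 2 days". It justifies the 2 days as slightly more than five half-lives when renal function is normal. It contains no rule for interruptions.

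The two sets of rates are meant to be read together. Section 8.7.4 says that the "respective incidence rate for the total study population (the complete set) will also be taken into account" when the sub-population rates are interpreted. Section 8.9 offers the same device against selection bias in the long-term sets: "A comparison with the incidence rate for the respective time window in the total population (the complete set").

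**The concern.** The first two undosed days of an allowed interruption are both inside the interruption, so not counted, and inside the 2-day post-stop period, so countable. Nothing says which rule wins.

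If the interruption rule wins, two things follow. First, events on those days leave the long-term sets, while 8.7.1 as written can keep the same events of the same patients in the complete set. The comparison that 8.7.4 and 8.9 rely on is then not like for like. Second, exposure status on a given day depends on what happens later, because the two days are excluded only if the patient restarts within 30 days. The half-life argument in 8.7.1 does not depend on a later restart.

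If adverse events are more frequent on those days than on dosed days, the rule lowers the long-term rates. That is the favourable direction in a long-term safety study.

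**Working it through.** The protocol states no figure on this point, and study size rests on no calculation (8.5: "The sample size is not based on any formal calculation"). There is nothing to reproduce. The check is a comparison of the rules, followed by arithmetic for scale.

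**1. The same event under the literal rules.** Take a patient already in the long-term set-12, with the last dose on day 0 and an adverse event dated to day 2.

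| Later course | 8.7.4, interruption rule prevailing | 8.7.1 |
|---|---|---|
| Restart on day 10 | Interruption of up to 30 days: not counted | Counted, if a short gap is a stop with a 2-day tail or is not cut out of exposure |
| Restart on day 40, or never | Not an allowed interruption: counted in the 2-day tail | Counted |

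Only the restart date differs between the rows. An event dated to day 0 is on treatment under every rule and is unaffected.

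**2. Possible readings for days 1-2.**

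- Interruption rule prevails in 8.7.4: the two sections differ.
- 2-day tail prevails in 8.7.4: the sections agree on events. Because the tail sentence there omits patient-time, numerator and denominator could still be mismatched.
- "Stop" means only a final stop or one of more than 30 days: 8.7.4 excludes the whole gap. 8.7.1 does not say whether a short gap is removed, so the sections agree only if the exclusion is carried into 8.7.1, where it is not written.

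**3. Patient-time involved.** The overlap is 2 days per interruption.

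- Share of the interruption: 2/30 = 6.7%; 2/14 = 14%; 2/7 = 29%; 2/2 = 100%.
- Share of a patient-year: 2/365.25 = 0.55%.
- Share of a 6-month window: 2/182.6 = 1.1%.

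The effect on the denominator is small.

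**4. Effect on the rate, by assumption.** None of these inputs is in the protocol: 20 on-drug events in 100 patient-years (PY), h = 10 to 100 interruptions, and x = 0 to 4 events dated to days 1-2.

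- Both days excluded: 20/100 × 100 = 20.0 per 100 PY.
- Both days counted, for events and time: (20 + x)/(100 + 2h/365.25) × 100.
- Events counted but time not: (20 + x)/100 × 100.

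| h | x | Excluded | Counted | Events only | Excluded/counted |
|---|---|---|---|---|---|
| 100 | 0 | 20.00 | 19.89 | 20.00 | 1.005 |
| 50 | 1 | 20.00 | 20.94 | 21.00 | 0.955 |
| 50 | 2 | 20.00 | 21.94 | 22.00 | 0.912 |
| 10 | 4 | 20.00 | 23.99 | 24.00 | 0.834 |

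For h = 50 the added time is 100/365.25 = 0.274 PY. At the on-drug rate one would expect 0.274 × 0.20 = 0.055 events there. Exclusion lowers the rate only if the events on those days exceed that number. With no such events it raises the rate very slightly.

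**The case against.** **The contradiction is not forced.** The second sentence of 8.7.4 begins with "only", so it can be read as a further restriction and not as an order to include. "Interruption" and "treatment stop" are different words, and 8.7.5 also draws a 30-day line: "The reasons for Kineret treatment discontinuation for more than 30 days will be summarized with number and percentage". This stands in part. A reconciling reading exists, namely that the 2-day period prevails, so a reader who inferred that the section cannot be applied at all would go too far. But 8.7.5 draws its line for reporting reasons and does not define a stop. The restrictive reading also leaves 8.7.4 and 8.7.1 different.

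**The loss from the complete-set comparison is conditional.** This is right. It needs 8.7.1 to treat a short gap as a stop with a tail, or not to remove it. Those are the readings open under its text, but the protocol does not choose between them.

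**Events that prompt an interruption may have begun before it.** This is also right. Section 10.2 says that onset dates are collected, and onset on or before the last dosing day counts under every rule. A reader might infer that such events typically fall at the start of the gap and that a sizeable share is lost. The protocol gives no data for either. Nor can the affected events be called drug-related, since 10.2 records events regardless of relation to Kineret.

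**The comparison is only descriptive.** True. There is no test or decision rule, and the early-versus-late comparison within a long-term set uses one rule in all windows. What is affected is the comparison with the complete set.

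**Day-level exposure rules belong in the SAP.** Often they do. Here the protocol itself fixes both sentences, so the SAP would have to override one of them.

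**Conclusion.** The point holds as a minor inconsistency. For the first two undosed days of a registered interruption of up to 30 days, the exclusion in 8.7.4 conflicts with the 2-day exposure period in the next sentence and in 8.7.1. Read literally, events on those days leave the long-term sets, can stay in the complete set, and count or not according to a later restart date.

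The likely consequence is a slight downward bias of the long-term rates in the planned comparison. This assumes that the interruption rule prevails in 8.7.4, that it is not carried into 8.7.1, and that events are more frequent on those two days than on dosed days. The size cannot be computed from the protocol. The ratios of 1.005 to 0.83 illustrate assumed inputs and are not estimates, and the true effect may be near zero. Only registered interruptions are concerned. Section 8.9 already acknowledges misclassification during unregistered ones, and this point does not bear on that.

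**What to change.** Replace the exclusion sentence in 8.7.4 with a rule such as: during an allowed interruption, adverse events and patient-time are counted for the first 2 days (the plan's own post-dose exposure period) and not thereafter until restart.

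Apply this one exposure rule to events and patient-time in 8.7.1, 8.7.2.1 and 8.7.4. In 8.7.3 apply it to event counting only, because the denominator there is a number of patients and not patient-time.

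The cost is one sentence and one common exposure derivation, with no new data. It should be settled before data extraction and carried into the SAP, which Annex 1 schedules for completion before data collection starts. The downside for the sponsor is that long-term rates may become slightly less favourable.
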